The first stage ITS analysis will consist of segmented regression with an autoregressive error model to account for the correlation between successive monthly ADRs. As described in the primary analysis, we will plot monthly ADRs for a random sample of endoscopists to guide our ITS modelling strategy. We will also use these plots to assess whether to include seasonal effects, which would be included as a categorical quarter variable in the model. We assume that a provider's observed number of positive screens during month t , $PositiveScreens_t$, follows a Poisson distribution with conditional mean λ_t . Our basic ITS model for λ_t for a particular provider has the following form: $\text{Log}(PositiveScreens_t) = \beta_0 + \log(TotalScreens_t) + \beta_1 Intervention_t + \beta_2 Time_t + \beta_3 Time\text{-}After\text{-}Intervention_t + \beta_4 Age + \beta_5 Sex + \beta_6 Race + \beta_7 Season_t$, where t indicates time coded in months.⁵⁵ In this ITS analysis, time is coded monthly and treated as a continuous variable instead of coding it as a categorical variable as in the stepped wedge analysis. The main predictors of interest will include the immediate intervention effect (*Intervention*) and whether the monthly post-intervention time trend differs from the pre-intervention time trend (*Time-After-Intervention*). Autocorrelation will be examined using residual plots and the Durbin-Watson or Durbin's alternative test and corrected using lagged study time variables as appropriate.⁵⁶ Each model will provide a RR estimate, 95% CI and p-value for a provider's intervention effect.

The second stage analysis will consist of random effects meta-regression to aggregate the provider intervention effects estimated from the first stage.^{61,62} This model will enable us to estimate the average intervention effect across providers accounting for heterogeneity at both the site and provider level by including random effects for both. We include a random effect for provider because although we have included the majority of the eligible providers in the VA system, we conservatively consider the providers included in our analysis to be a random sample from the full possible set of providers.⁶⁴ Konstantopoulos et al. describe a similar multilevel meta-regression analysis where studies are nested within school districts – here we have providers nested within sites.⁶⁵ Our meta-regression model will adjust for the variables used in the randomization stratification procedure (*Volume2018*, *ADR2018*, and *ADRMeasured*), provider-level variables (baseline years in practice and baseline annual procedure volume), and site level characteristics including [split dose bowel preparation protocols (SDBP) in 2018,] urban/rural and cumulative annual procedure volume.

Power Calculation: Our power calculation for the overall intervention effect is estimated from an ITS model after accounting for 5% data loss at the site level and 8% provider attrition. On average a provider has 19.5 months of data in both the pre-intervention and post-intervention periods. Thus we estimate 386 patients/provider or 220,215 patients seen in each period. Again, the number of patients is included in the power calculation because the number of patients seen by providers greatly affects the power of our design. To estimate power, we simulated ITS data with varying intervention effect sizes adapting code provided by Rozario et al.⁶⁶ Under an ITS model with an autocorrelated error structure, we expect to achieve 96.8% power to detect a 1.25% increase in ADR from a pre-intervention rate of 27.5% (based on 1000 simulations). Power calculations were conducted in SAS v 9.0.

Explanatory Analysis – Stepped Wedge and ITS analyses at the Patient Level: One potential limitation of the analyses described above is that we are aggregating patient-level data to the provider month-level. The analysis of aggregated data is susceptible to Simpson's paradox, where the direction of a relationship between an exposure and outcome can change when the data is analyzed at an aggregated level versus a partitioned level.^{67,68} This is due to insufficient adjustment for confounders when the data is analyzed at the aggregated level. The ITS analysis is particularly vulnerable to Simpson's paradox as there is no comparison of intervention and controls at the same point in time, but rather this analysis focuses on pre/post comparisons within providers. Thus, there is potential for confounding due to case-mix differences in patients seen at different points in time. To overcome this paradox, we will re-examine both our primary stepped wedge analysis and our secondary ITS analysis using data at the patient observation level. The modeling will be very similar, where we will use Poisson outcome models, but there will be no offset term at the patient level. The interpretation of the results will be the same as before. For the stepped wedge analysis, the exponentiated coefficient of intervention will represent the ratio of the screening rate after implementing the intervention versus before, for a given provider. For the ITS analysis, the first stage modeling will yield the ratio of each providers screening rate after implementing the intervention versus before. The second stage will yield a pooled estimate of the intervention RR across providers.

Aim 2: Evaluation of VA-EQuIP implementation

[Evaluation Overview: We will use a mixed-methods approach to perform the evaluation. This multi-faceted evaluation consists of three components: monitoring of VA-EQuIP usage statistics, pre/post surveys of quality stewards and providers, and qualitative interviews with quality stewards and individual providers. The approach will capture key RE-AIM (1a) and COM-B (1b) domains with qualitative assessments to explore barriers and facilitators to implementation and components of provider behavior change.]

Evaluation Measures and Outcomes:

Aim 2a: The evaluation measures will include reach, adoption, implementation, and maintenance domains (**Appendix 5**). Reach will be measured with site practice characteristics items from the baseline quality steward survey. We will also evaluate claims data from CDW fee basis, VA Choice and MISSION Acts, and contracting records to determine the proportion of Veterans at each facility who have colonoscopies performed by VA versus non-VA (community care) providers (another reach measure). Our comprehensive data infrastructure allows us to electronically monitor VA-EQuIP quality data views by site and provider (our primary adoption measure). These data will be used as quantitative, continuous measures of adoption at both the site and individual provider level. We will also collect participant data from those sites and providers participating in collaborative learning sessions. We will also include additional adoption measures in the quality steward

surveys by asking about use of VA-EQuIP for quality measurement and reporting at each site. As for implementation measures, the centralized VA-EQuIP infrastructure will also allow us to capture fidelity by assessing timing of delivery of the intervention (fidelity). The quality steward surveys were designed to capture outcome measures for sites (e.g. change in bowel preparation protocols) before and after VA-EQuIP implementation (**Appendices 6-7**). Qualitative interviews with quality stewards will explore site level barriers and facilitators to VA-EQuIP implementation and start after the last collaborative learning session for each randomized cluster.

[Aim 2b: The provider surveys and qualitative interviewers were designed to capture components of behavior change mapped to domains of the COM-B model (e.g. capability: knowledge of colonoscopy techniques to enhance adenoma detection) before and after VA-EQuIP implementation (**Appendices 6-7**). Provider qualitative interviews will start after the last collaborative learning session for each randomized cluster.]

Quantitative Survey Design and Qualitative Interview Guide: [Our quantitative surveys for quality stewards and individual providers include measures we have defined for each domain. Surveys will be delivered pre- and post (12 months) VA-EQuIP implementation; interviews will be conducted after each randomized cluster through trial completion.] A full description of all data sources, measures, outcomes, quantitative surveys, and qualitative interview guide are available in **Appendices 5-8**. We have developed draft survey questionnaires for quality stewards [and providers and a provider interview script to capture the intended constructs of our conceptual framework.] Because our measures are specific to the VA-EQuIP intervention, it was necessary to develop specific questionnaire items with our co-investigator and survey design expert [name]. Development has been an iterative process, wherein all necessary constructs and domains were identified and appropriate questions for capturing these domains were constructed (see draft, **Appendix 6-7**). The quality steward surveys will assess site characteristics (RE-AIM) and colonoscopy protocols before and after VA-EQuIP implementation for use in assessing site level change after implementation. Practice changes include whether or not sites changed clinical protocols or practice, including quality measurement practices, quality reporting practices, bowel preparation protocols, endoscopy technique (e.g. withdrawal time), use of assist devices marketed to improve adenoma detection (e.g. cap), or seeking additional training or proctoring. The provider survey was modified from a previously developed, validated COM-B-based survey⁶⁹ to capture behavior change domains consistent with our conceptual model. Qualitative interviews with stewards will explore barriers and facilitators of VA-EQuIP implementation (RE-AIM QuEST).⁶⁹ Qualitative interviews with providers will explore components of behavior change related to VA-EQuIP implementation (**Appendix 8**).

Quantitative Survey Administration: The quantitative surveys will be delivered to the identified local quality stewards (N=73) and providers (N=657) for each enrolled site via the Research Electronic Data Capture (REDCap)⁷⁰ platform at baseline (prior to VA-EQuIP) and 12 months following completion of the VA-EQuIP intervention. We will incorporate established methods of maximizing web survey responses, including multiple, carefully-timed, integrated email contacts.⁷¹

Qualitative Interviews and Transcription: Trained interviewers, supervised by [name], will conduct and audio record up to 60-minute telephone interviews with individual endoscopists at participating facilities. All interviews will be transcribed verbatim by the VA Health Services Research and Development (HSR&D) Centralized Transcription Services Program (CTSP), directed by [name] and located in Salt Lake City. Purposive sampling⁷² will create the sample needed for interviewing endoscopists at the facilities. Based on principles of thematic saturation (the concept that no new themes emerge from subsequent interviews), we will estimate a minimum sample size of at least 50 persons (**25 quality stewards and 25 individual providers**) across the sites enrolled in our study, with plans to evenly distribute interviews between high and low performing providers and at least 2 sites per VISN. Given the two cohorts of providers at high and low performing sites geographically dispersed across the country, our sample size has been chosen to ensure saturation.⁷³ We will continue with interviews until thematic saturation has been reached.⁷³

Analysis

VA-EQuIP Statistics: To evaluate VA-EQuIP adoption and implementation we will continuously monitor the number of providers viewing VA-EQuIP dashboards and participating in collaborative learning sessions through 12-month assessment time points. Descriptive statistics will be performed at both the site and provider level.

Survey analysis (Baseline and 12 month outcomes): [Survey data analysis will include descriptive statistics of quality steward and individual provider survey responses at two timepoints: baseline and 12 months after VA-EQuIP implementation. These will include response distributions/percentages or means and standard deviations for all baseline site characteristics and all implementation and behavior change measures. We will examine what percent of providers viewed their quality data and if site-level activities that could impact provider behavior (“opportunities”) had been initiated after the intervention. Using the quality steward survey, we will assess the proportion of sites exhibiting changes in protocols and be able to assess sustainability of new practices invoked earlier in the intervention. We will summarize responses for the provider survey using the scoring approach from the COM-B survey that we adapted for our provider survey, and will compare responses from the baseline and 12-month surveys. We will also compare COM-B measures between providers, stratified by ADR categories (e.g. quintiles) pre- and post-VA-EQuIP and by involvement in collaborative learning as a categorical variable.]

Qualitative analysis: Qualitative interviews will be analyzed using the verbatim transcripts for codebook construction using the qualitative “editing” method by Crabtree and Miller.⁷⁴ Representative quotations will be captured verbatim using Atlas.ti (Scientific Software, Berlin Germany) [and mapped to COM-B behavior change domains.] Working with [name], two extensively trained qualitative analysts will meet and process any differences until they agree. The codes determined through this agreement process will be recorded in a master file and become the basis for the final analysis. This process of coding independently (the basis for the inter-coder reliability scores) and then discussing each case will ensure narrative coherence in the coding process. Inter-coder reliability kappa scores of below 0.61 will trigger a training meeting. This process has consistently achieved an inter-coder reliability kappa score of ≥ 0.70 .⁷⁵

NEXT STEPS

Standardized, transparent, automated quality reporting is the first step to ensure and improve colonoscopy quality. [Due to the sensitive nature of provider quality metrics, heterogeneity of VA sites, and desire to maintain local autonomy, we postulate that the collaborative learning sessions will help drive peer-to-peer and peer-to-expert learning to impact quality improvement in a non-punitive forum.] The interactive problem solving and support in our collaborative learning represents a limited form of external facilitation. **A critical next step will be to provide access to more intensive interventions, such as site visits and hands-on training, for persistently low performing providers based on findings from our evaluation.** Research has demonstrated that colonoscopy quality can be improved through a short course to train colonoscopists how to perform a higher quality exam.³¹ The national GI program office is still planning a joint training program with VA’s Employee Education System (EES) for colonoscopists in order to improve the quality of colonoscopy in VA and ultimately, Veterans’ health outcomes. The training will take advantage of lessons learned from the Kaminski study³¹ and would be co-directed by Drs. [name] (Co-PI) and [name] (Co-I) in collaboration with leadership of the SimLEARN Center (Orlando, Florida). Highly qualified faculty will be recruited from across VA to lead a 1.5-day course comprised of didactic lectures and hands-on skills enhancement for approximately 50 VA colonoscopists. Future training programs of this type are likely to be needed given the large number of providers performing colonoscopy in VA. Adding hands-on-training to VA-EQuIP will be the critical next step for improving refractory colonoscopy quality deficiencies identified after VA-EQuIP implementation. An additional next step is to report over and underuse of colonoscopy to improve access to GI specialty care. The National GI Access initiative ([name]) is developing measures of access and overuse of colonoscopy. In collaboration with [name] office, VA-EQuIP can ensure that access initiatives are focused on providing Veterans with high quality procedures. If validated overuse measures become available in the VA-CDW we would be able to incorporate them into VA-EQuIP.

DISSEMINATION PLAN

Our strong partnership with the Measurement Science QUERI and national GI program office will provide ongoing dissemination throughout the project via print and electronic publications. We will post news about progress of the project on both the Measurement Science QUERI Web Site and National GI Sharepoint Site. We will alert VA stakeholders to new postings via electronic internal news releases. At the conclusion of the project, Drs. [name] and [name] will collaborate with [name] to produce a VA HSR&D CyberSeminar to notify critical VA stakeholders of the findings. Our leadership team and members of the GI Field Advisory Committee will participate in the seminar development. Specifically, they will help formulate the implications from the study and key members of our team will be available during the CyberSeminar to answer questions.

All slides and formal notes will be posted on the Gastroenterology Program SharePoint site, ensuring their continued availability for VA providers. We plan similar presentations for the American Gastroenterology Association and American College of Gastroenterology. The academic and research communities beyond VA will be reached through traditional means, including publication in high impact peer-reviewed journals specific to the field, such as *Gastroenterology* and the *American Journal of Gastroenterology*. Results will be presented at national conferences hosted by VA HSR&D and AcademyHealth. Policy makers and others (e.g. Office of Specialty Care) in a position to affect clinical care will be reached through a policy brief, which we will distribute in collaboration with the national GI program office to researchers, federal, state, and local elected leaders, and Veterans' organizations.

SAMPLE RECRUITMENT

Recruitment timeline / detailed monthly plan for sample recruitment: The implementation strategy timeline and monthly plan for the trial is shown in **Figures 3 & 5**. VA-EQuIP dashboards will be delivered in 6 waves of 12-13 sites (N=73). We will deliver our quality steward and provider surveys before and at 12 months after each cluster in our stepped wedge design to study completion. We will recruit endoscopists for qualitative interviews starting at 12 weeks (after VA-EQuIP intervention) and conduct 2-5 interviews per cluster until study completion.

Pitfalls / Alternative plans if sample recruitment does not meet expectations:

For Aim 1, we have accounted for provider attrition and problematic data in our power calculation, based on our own and historical data provided by the national GI program office. The centralized infrastructure and NLP pipelines of VA-EQuIP will allow creation of reports for all providers in our database to ensure that the NLP system performance remains high throughout the project, several internal validation studies are planned. Each validation will involve a manual annotation of a random set of notes selected at each of the participating sites to create a reference standard. The system performance metrics will be calculated by comparing NLP system output and the reference standard. Since the NLP system was extensively evaluated during development, validation will be limited to measuring precision of extraction. If precision of extraction of each of the variable stays above 90%, the NLP system will be applied on the colonoscopy reports without changes. If evaluation detects decreased precision, detailed error analysis will be performed and system adaptation might be required. If system adaptation is performed, another round of validation will be required. In this case, both precision and recall will be evaluated. Colonoscopies performed on Veterans by providers outside of VA could be assessed for quality metrics using the NLP system contingent on the future integration of the colonoscopy and pathology data into VA CDW.

For Aim 2, our pre-implementation work provides strong evidence that our team is capable of performing the evaluation and maximizing survey response and qualitative interview completion. Our published needs assessment survey¹⁸ had a response rate of 69% facilitated by 3 electronic reminder emails. We anticipate an even higher response rate for this project as the prior work required updating of outdated contact information, which is now available to us. For the qualitative work to determine barriers to quality reporting we obtained 21 interviews in <3 months with only single email invitations to VA sites. If survey response rates are not meeting expectations with electronic reminders, we will contact the local stewards by telephone to assess technical or other issues with the survey. The GI program office will promote and encourage survey response and interview follow up. A limitation of our study is that we are not currently able to measure quality for community care colonoscopies, yet we do plan on assessing the proportion of community care colonoscopies performed for future efforts to incorporate community care colonoscopy quality into VA-EQuIP.

PROJECT MANAGEMENT PLAN

Drs. [name] and [name], who have worked closely together over the past five years with multiple site visits between their VAs, will be responsible for overseeing all aspects of the project, including achievement of the project aims, conducting the quantitative and qualitative analyses, timely provision of project deliverables, coordination of the project team and workgroups, incorporation of feedback from the Steering Committee, and facilitation of partnerships with the national GI program office and FAC, QUERI, and other VA constituents. The Steering Committee (Drs. [name], [name], [name], [[name]], [[name]], [name], and [name]) will meet virtually monthly to review all major decisions, monitor the project's progress in meeting recruitment and other goals, to review the data analysis and findings, and coordinate publications and other products. The project aims will be advanced by 3 workgroups. Inclusion of Drs. [name] and [name] on each workgroup will

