We created an operational database of colonoscopy procedures and linked pathology notes housed in the VA CDW Text Integration Utility that can be semi-automatically updated with the most current data across the VA healthcare system. We have optimized a machine learning document classifier that uses the support vector machine algorithm to delineate a note as either a colonoscopy procedure note, or not. Our process allows to rapidly and prospectively confirm colonoscopy notes for NLP processing and colonoscopy quality reporting. Our NLP pipelines to extract colonoscopy procedure and pathology data have excellent performance (Table 1). The VA-EQuIP dashboard visually presents biannual and cumulative colonoscopy quality metrics to VA sites and providers, and provides comparison metric data at the local site and national level (Figure 2). All reports are created using Microsoft™ SQL Server Reporting Services 2013 and are hosted on a Microsoft SharePoint 2013 internal website. Access is controlled by both SharePoint memberships and local data access permissions.

Usability and [Pilot] Testing: In cooperation with our operations sponsor and partner, we obtained feedback and usability information on VA-EQuIP from the GI Field Advisory Committee. The committee members were provided access to their sites and individual data on colonoscopy quality. Respondents (N=5) provided feedback for internal consistency and were surveyed via the System Usability Scale (SUS).⁴⁹ The average SUS score for VA-EQuIP for 5 respondents was 87.0 (SD 9.9, range 77.5-100). A score >80.3 has been found to be in the top 10% of usability performance based on an ev

Table 1: NLP Performance for Colonoscopy Quality Metrics

Variable	PPV	Sensitivity	F Measure
ADR	98%	100%	99%
Screening Indication	89%	100%	94%
Cecal Intubation Rate	98%	99%	99%
Bowel Prep Adequate	100%	100%	100%

ates for NLP processing and colonoscopy quality reporting. and pathology data have excellent performance (**Table**

Facility Name:North Hospital **Provider Name:** Dr. C **Report Year:** 2017

[figure not shown]

Figure 2: VA-EQuIP Quality Dashboard

RESEARCH OVERLAP

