Power Calculation: Our power calculation for the intervention effect comes from a stepped wedge model. Based on 2017 data there were 73 sites with 657 providers performing 155,926 cases per year in our sampling frame. We estimate a 5% loss of site data due to data quality issues. We also estimate a provider attrition rate of 8% from four years of data provided by the national GI program office where attrition rates ranged from 6.9-12%.¹⁵ After accounting for data loss and provider attrition, we expect 69 sites with 571 providers seeing 135,517 patients/year, corresponding to 95 providers/wave and 59 patients/provider/quarter. Note that the number of patients seen by providers factors into our power calculation as it affects the standard errors of the intervention effect, where seeing more patients yields greater power. Our primary outcome is ADR, which we will conservatively estimate as having a range of 13-79% based on prior research^{7,8} and our preliminary data. For cluster randomized trials using implementation designs such as ours, the intra-cluster correlation coefficient (ICC) estimates for patient outcomes are approximately 0.030.⁵⁸ Based on an ADR of 27.5% in the pre-intervention period, we would have about 93% power to detect a 1.0% absolute increase in ADR. This difference is clinically important, because a 1% increase in ADR is associated with a 3.0% decrease in risk of incident CRC, and a 5% decrease in risk of fatal interval CRC.⁷ Power calculations were conducted in R using the swCRTdesign package, and are conservative due to exclusion of three quarters of baseline data, and because the second level of clustering by provider is not considered.^{59,60}

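### The 90% precision rule for the NLP is wider than the 1.0-point ADR effect the trial is powered for, and it does not compare control with intervention notes

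*Combined protocol and SAP*

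**What the plan says.** Under the heading on developing a quality monitoring system, the protocol states "Our NLP pipelines to extract colonoscopy procedure and pathology data have excellent performance (Table 1"). Table 1 reports PPV 98%, sensitivity 100% and F measure 99% for ADR. For screening indication the PPV is 89%.

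The in-trial check is in Sample Recruitment, in the Aim 1 paragraph of the pitfalls subsection. Several validations are planned, each on randomly chosen notes from every participating site, and "validation will be limited to measuring precision of extraction". The decision rule is "If precision of extraction of each of the variable stays above 90%, the NLP system will be applied on the colonoscopy reports without changes". It continues: "If evaluation detects decreased precision, detailed error analysis will be performed and system adaptation might be required". Recall is assessed only after the system has been adapted. The available text gives no limit specific to the adenoma variable, no validation sample size, no comparison of precision by rollout status and no correction of ADR for misclassification.

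The Aim 1 stepped wedge power calculation sets the benchmark: "Based on an ADR of 27.5% in the pre-intervention period, we would have about 93% power to detect a 1.0% absolute increase in ADR". The primary model adjusts for study quarter as a categorical term common to all sites.

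**The concern.** The primary outcome is produced by the NLP system, so its error rate is part of the measurement. One limit covers every variable, and for the adenoma variable it leaves almost 8 points of slack below the reported 98%. The trial is designed to detect a 1-point change in ADR.

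What matters is whether error differs between control and intervention notes. A difference tied to rollout has the same pattern over sites and time as the intervention indicator, so the primary model would count it as an intervention effect. The interrupted time series, the GEE fallback and the patient-level re-analysis would not expose it, because all use the same NLP-derived outcome. A validation result that mixes control and intervention notes could also conceal it: with equal numbers of NLP-positive notes, 98% before and 83% after average 90.5%, which passes.

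**Working it through.** **Inputs.** PPV 98% and sensitivity 100% (Table 1); 90% limit (Sample Recruitment); ADR 27.5%, target 1.0 point and power of about 93% (Aim 1 power calculation). On size, "we expect 69 sites with 571 providers seeing 135,517 patients/year, corresponding to 95 providers/wave and 59 patients/provider/quarter"; on clustering, "the intra-cluster correlation coefficient (ICC) estimates for patient outcomes are approximately 0.030". Assumed: two-sided alpha 0.05, since none is stated, and PPV measured per colonoscopy.

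**The plan's own figures.**
- F for ADR = 2 × 0.98 × 1.00 / 1.98 = 0.990, as in Table 1.
- Power was recomputed with the usual stepped wedge variance: random cluster intercept, categorical quarters, six waves, one baseline quarter and 3 to 4 follow-up quarters. Residual variance is 0.275 × 0.725 per patient, and between-cluster variance is 0.03/0.97 of that.
- Provider clusters (95 per wave, 59 patients per quarter) give 92.9% to 93.6%. Site clusters (69/6 = 11.5 per wave, 135,517/69/4 = 491 per quarter) give 92.6% to 93.5%. The stated 93% is reproduced.
- These versions count the rollout quarter as exposed. Discarding it, as the design section plans, gives about 80% to 82%. That is a separate matter and does not change the 1.0-point benchmark.
- The standard error implied by 93% power is 1.0 / (1.96 + 1.476) = 0.29 points.

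**Effect of precision on measured ADR.** True positives are ADR × sensitivity, and NLP positives are true positives / PPV. So measured ADR = true ADR × sensitivity / PPV. With true ADR 27.5% and sensitivity 100%:

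| PPV | Measured ADR | Shift from PPV 98% | False positives, % of exams |
|---|---|---|---|
| 98% | 28.06% | – | 0.56 |
| 96% | 28.65% | 0.58 | 1.15 |
| 95% | 28.95% | 0.89 | 1.45 |
| 94.6% | 29.06% | 1.0 | 1.56 |
| 93% | 29.57% | 1.51 | 2.07 |
| 90.1% | 30.52% | 2.46 | 3.02 |
| 90% | 30.56% | 2.49 | 3.06 |

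The 1.0-point row solves 0.275 / (0.2806 + 0.010) = 0.946. If 27.5% is instead the rate as measured at PPV 98%, the last shift is 27.5 × 0.98/0.90 − 27.5 = 2.44 points. Across true ADRs of 20% to 40% the last shift runs from 1.8 to 3.6 points. As a rate ratio it is 0.98/0.90 = 1.089, against 28.5/27.5 = 1.036 for the target.

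**What the primary model would do with it.** The expected stepped wedge estimate was computed on the linear scale with no true effect. With PPV at 90% only after rollout, it is 2.49 points, the full shift. With the same fall following calendar time at all sites, as a step or a straight line, it is 0.00.

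**Risk of a false positive trial.** With a standard error of 0.29, no true effect and the fall confined to post-rollout notes, PPV 96% gives a significant result about half the time and PPV 95% about 86% of the time. Both pass the rule.

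**Dependence on sensitivity.** With post-rollout PPV 90%, sensitivity 95% gives 0.275 × 0.95/0.90 = 29.03%, a net shift of 0.97. Sensitivity 92% gives 28.11%, a net shift of 0.05.

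**The case against.** The strongest reply is that nothing in the documents predicts such drift. A reader might infer that the collaborative learning changes how endoscopists describe polyps, and so the text the NLP reads. Table 2 does not support that: it lists bowel preparation, polyp identification and examination technique, and nothing on describing or documenting findings. Adenoma status also needs histology, and the intervention is not aimed at pathologists. The Significance section does mention more standardised documentation as a possible use of the quality data, but that is a hope for the system and not an intervention component.

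Size is a second difficulty. Reaching PPV 90% needs false positives to rise from 0.56% to 3.06% of exams, 5.4-fold, in post-rollout notes only. Even the 1.0-point case needs 1.56%, a 2.8-fold rise. If false positives merely scaled with the number of non-adenomatous polyp reports, 20% more reports would add 0.56 × 0.20 = 0.11 points and 50% more would add 0.28. A reader might therefore take 2.5 points as an expected bias. It is the outer edge of what the rule permits, with sensitivity held at 100%.

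Third, the validation text can be read more favourably. It does not say that results are pooled over sites or dates, and error analysis could be triggered by any decrease in precision. But the sentence before that permits use without changes above 90%, and adaptation is only a possibility even after a decrease.

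These replies limit the claim. They do not supply the missing comparison between control and intervention notes.

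**Conclusion.** The concern holds as a gap in a safeguard. For the adenoma variable the rule tolerates a loss of precision that, if confined to post-rollout notes, would produce a shift equal to the 1.0-point target at PPV of about 94.6%, and up to about 2.5 points just above 90%. This rests on ADR 27.5%, constant sensitivity, PPV per colonoscopy and drift tied to rollout. Drift shared across sites is removed from the primary estimate. A simultaneous loss of recall would offset the shift, to about zero at 92% sensitivity, but the plan would not measure it.

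The documents do not support a statement that the trial's estimate is biased, or that rollout will change precision. The size of any real drift is unknown.

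A smaller inconsistency stands on its own: screening indication starts at 89% PPV, already below the limit set for every variable, and screening ADR is one of the two primary outcomes.

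**What to change.** Amend the validation paragraph in Sample Recruitment:

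1. Draw the validation notes at each site from both control and intervention months, and report adenoma precision by rollout status, pooled across sites.
2. For the adenoma variable, replace the uniform 90% limit with a trigger on the control-versus-intervention difference, set so that the implied ADR shift is clearly below 1.0 point. For scale, a 0.5-point shift corresponds to PPV 0.275 / (0.2806 + 0.005) = 96.3%, a difference of 1.7 points. Do not apply a fixed PPV floor site by site, because PPV depends on site ADR. The false-positive rate behind 98% at ADR 27.5% is 0.56/72.5 = 0.77% of non-adenoma exams. At ADR 13% the same rate gives 0.13 / (0.13 + 0.0077 × 0.87) = 95.1% with no drift.
3. Include NLP-negative exams so that recall can be checked, and report the primary rate ratio corrected for measured misclassification by rollout status as a sensitivity analysis.
4. Reconcile the 89% PPV for screening indication with the 90% rule.

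**Cost.** The design and primary model are unchanged. Ten NLP-positive exams per site per period (73 × 10 = 730) estimate the precision difference to 1.96 × √(2 × 0.98 × 0.02/730) = ±1.4 points, ignoring site clustering. Found by simple random sampling, 730 positives need about 730/0.2806 = 2,600 exams per period, and that sample would also supply negatives. A true difference equal to the trigger is flagged only about half the time, so trigger and sample size should be chosen together. Because no validation sample size is stated, some extra annotation may be needed, and error analysis may be triggered more often.
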